5.6.1 Management of Infusion Reactions for Pembrolizumab

Signs and symptoms usually develop during or shortly after drug infusion and generally resolve completely within 24 hours of completion of infusion. The table below outlines guidelines for subjects who experience an infusion-related reaction to pembrolizumab administration.

NCI CTCAE Grade	Treatment	Premedication at subsequent dosing
Grade 1 Mild reaction; infusion interruption not indicated; intervention not indicated	Increase monitoring of vital signs as medically indicated until the subject is deemed medically stable in the opinion of the investigator.	None
Grade 2 Requires infusion interruption but responds promptly to symptomatic treatment (e.g., antihistamines, NSAIDS, narcotics, IV fluids); prophylactic medications indicated for ≤ 24 hrs	
Stop Infusion and monitor symptoms. Additional appropriate medical therapy may include but is not limited to: IV fluids, antihistamines, NSAIDS, acetaminophen, narcotics.
 
Increase monitoring of vital signs as medically indicated until the subject is deemed medically stable in the opinion of the investigator.
 
If symptoms resolve within 1 hour of stopping drug infusion, the infusion may be restarted at 50% of the original infusion rate (e.g. from 100 mL/hr to 50 mL/hr). Otherwise dosing will be held until symptoms resolve and the participant should be premedicated for the next scheduled dose.
 
Participants who develop Grade 2 toxicity despite adequate premedication should be permanently discontinued from further study drug treatment.
	
Subject may be pre-medicated 1.5h (± 30 minutes) prior to infusion of pembrolizumab with:
 
Diphenhydramine 50 mg po (or equivalent dose of antihistamine).
 
Acetaminophen 500-1000 mg po (or equivalent dose of antipyretic).

NCI CTCAE Grade	Treatment	Premedication at subsequent dosing
Grades 3 or 4 Grade 3: Prolonged (i.e., not rapidly responsive to symptomatic medication and/or brief interruption of infusion); recurrence of symptoms following initial improvement; hospitalization indicated for other clinical sequelae (e.g., renal impairment, pulmonary infiltrates) Grade 4: Life-threatening; pressor or ventilatory support indicated	Stop Infusion. Additional appropriate medical therapy may include but is not limited to: IV fluids, antihistamines, NSAIDS, acetaminophen, narcotics, oxygen, pressors, corticosteroids, epinephrine**. Increase monitoring of vital signs as medically indicated until the subject is deemed medically stable in the opinion of the investigator. Hospitalization may be indicated. **In cases of anaphylaxis, epinephrine should be used immediately. Subject is permanently discontinued from further trial treatment administration.	No subsequent dosing
Appropriate resuscitation equipment should be available at the bedside and a physician readily available during the period of drug administration. For further information, please refer to the Common Terminology Criteria for Adverse Events v5.0 (CTCAE) at http://ctep.cancer.gov .		

- c) If locally required, in accordance with Clinical Trial Facilitation Group (CTFG) guidelines, acceptable hormonal contraceptives are limited to those which inhibit ovulation.

5.6.3 Use in Pregnancy

If a subject inadvertently becomes pregnant while on treatment with pembrolizumab/entinostat, the subject will immediately be removed from the study. The site will contact the subject at least monthly and document the subject's status until the pregnancy has been completed or terminated. The outcome of the pregnancy will be reported to SYNDAX without delay and within 24 hours to the Sponsor and within 2 working days to SYNDAX, if the outcome is a serious adverse experience (e.g., death, abortion, congenital anomaly, or other disabling or life-threatening complication to the mother or newborn).

The study investigator will make every effort to obtain permission to follow the outcome of the pregnancy and report the condition of the fetus or newborn to the Sponsor. If a male subject impregnates his female partner, the study personnel at the site must be informed immediately and the pregnancy reported to SYNDAX, as described above and in Section 8.4.

5.6.4 Overdose of Pembrolizumab

For purposes of this study, an overdose of pembrolizumab will be defined as any dose of 1,000 mg or greater (≥ 5 times the indicated dose). No specific information is available on the treatment of overdose of pembrolizumab. In the event of overdose, the participant should be observed closely for signs of toxicity. Appropriate supportive treatment should be provided, if clinically indicated.

If an AE(s) is associated with ("results from") the overdose of pembrolizumab, the AE(s) is reported as a SAE, even if no other seriousness criteria are met.

5.6.5 Overdose of Entinostat

There is no information on overdose of entinostat. Any SAE that occurs at any dose level of entinostat should be reported to SYNDAX Pharmaceuticals. Refer to section 8.4 for additional details on AE reporting requirements.

5.7 Other Modalities or Procedures

5.7.1 On-Entinostat Treatment Biopsy (Day 22 (\pm 2 days))

A mandatory on-entinostat treatment tumor biopsy will be performed in the end of cycle 1, beginning of cycle 2 (day 22 \pm 2 days), immediately before concurrent entinostat-pembrolizumab treatment. Depending on the location of the tumor, the biopsy can be a core, excisional, or punch and performed as an outpatient procedure at the bedside (if palpable; e.g. subcutaneous, cutaneous, or palpable lymph node or CT-guided by interventional radiology). The tumor must be accessible for biopsy in a location considered safe for biopsy. Lung metastases should not be biopsied due to risk of pneumothorax.

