4.1 Inclusion Criteria

- 4.1.1 Age \geq 18 years at the time of consent.
- 4.1.2 Subject has provided informed consent and HIPAA prior to initiation of any study-specific activities/procedures.
- 4.1.3 ECOG Performance Status of ≤ 2 .
- 4.1.4 Histologically confirmed metastatic (regional or distant) melanoma of any subtype (cutaneous, mucosal, ocular).
- 4.1.5 AJCC stage unresectable III or stage IV disease that is measurable by RECIST v1.1 criteria.
- 4.1.6 Must agree to undergo one on-treatment tumor biopsy on day 22 (± 2 days) of the study. Subjects for whom fresh samples cannot be safely provided (e.g., inaccessible tumor for biopsy) will not be eligible for study participation.
- 4.1.7 Must have available archival tissue and subjects must have consented to allow collection of archived tumor blocks from previous surgeries confirming or treating unresectable stage III or distant metastatic disease. If more than one archived tumor block is available, only one block is required to be analyzed for the presence of TIL/TALS. Archived tumor tissues must fulfill the following criteria based on two representative H&E-stained tissue sections: (1) the tumor surface area must be at least 1cm^2 (which can be from a combination of metastatic blocks if necessary), (2) no more than 20% of necrosis, (3) the ratio of viable tumor cells to tumor-associated stroma should be at least 60/40, and (4) if TILs are present based on H&E stained

sections, they must be $\leq 1\%$ of the total number of cells in the specimen; the amount of tissue should be ≥ 1 cm².

[name], study pathologist, must sign off on the eligibility of archived tumor blocks before study enrollment. If archival tissue is unavailable or insufficient, fresh biopsy should be performed to confirm unresectable stage III or distant metastatic disease.

4.1.8 Previous treatment with immune checkpoint inhibitors and chemotherapies is allowed on condition that the last treatment is at least 28 days prior to first dose of entinostat. Previous treatment with targeted therapies (e.g. MAPK inhibitors) is allowed on condition that the last treatment was administered at least 15 days prior to first dose of entinostat).

4.1.9 Demonstrate adequate organ function as defined in the table below; all screening labs to be obtained within 21 days prior to entinostat treatment.

System	Laboratory Value
Hematological*	

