6.5.2 Mandatory On-Treatment Biopsy

A mandatory (excisional, punch or CT-guided) biopsy will be obtained in the end of cycle 1, beginning of cycle 2 (day 22±2 days), immediately before concurrent entinostat-pembrolizumab treatment.

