7.4.2 Study Day 22 ± 2 days (D1 of Cycle 2/Week 4)

1. Clinical evaluation: focused history and physical exam,
2. ECOG performance status,
3. 12-lead ECG,
4. Laboratory studies:
 - Hematology
 - Serum Chemistries
 - Collect peripheral blood for isolation of PBMCs (approximately 50 mL)
5. Mandatory Fresh Tumor biopsy (excisional, punch, or CT-guided),
6. Concomitant medication review,
7. Toxicity Assessment,
8. Patient pill diary check,
9. Entinostat administration: 5mg PO to be administered after mandatory biopsy; also dispense two 5-mg pills for administration on D28 and D35,
10. Pembrolizumab administration: 200 mg IV dose; to be administered after mandatory biopsy and after entinostat intake.

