7.8.2 Baseline Documentation of Target and Non-Target Lesions

All measurable lesions up to a maximum of 5 lesions total (and a maximum of two lesions per organ) representative of all involved organs should be identified as target lesions and will be recorded and measured at baseline.

Target lesions should be selected on the basis of their size (lesions with the longer diameter), growth rate at the time of study enrollment (stable or regressing tumor lesions should be excluded, irrespective of other parameters), be representative of all involved organs, and, in addition, should be those that lend themselves to reproducible repeated measurements.

A sum of the diameters (longest for non-nodal lesions, short axis for nodal lesions) for all target lesions will be calculated and reported as the baseline sum diameters. If lymph nodes are to be included in the sum, only the short axis is added into the sum. The baseline sum diameters will be used as reference to further characterize the objective tumor response of the measurable dimension of the disease.

All other lesions (or sites of disease), including pathological lymph nodes, should be identified as non-target lesions and should also be recorded at baseline. Measurements are not required and these lesions should be followed as “present” or “absent”, or in rare cases “unequivocal progression”.

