7.8.3 Evaluation of Target Lesions using RECIST 1.1 Criteria

NOTE: In addition to the information below, also see section 4.3.2 in the international criteria proposed by the Response Evaluation Criteria in Solid Tumors (RECIST) Committee, version 1.1¹⁵⁰ for special notes on the assessment of target lesions.

Complete response (CR) – Disappearance of all target lesions. Any pathological lymph node (whether target or non-target) must have decreased in short axis to <10 mm.

Partial response (PR) – At least a 30% decrease in the sum of the LD of the target lesions taking as reference the baseline sum LD.

Progressive Disease (PD) – At least a 20% increase in the sum of the LD of the target lesions taking as reference the smallest sum LD recorded since the treatment started including baseline if that is the smallest on study. In addition to the relative increase of 20%, the sum must also demonstrate an absolute increase of at least 5 mm. The appearance of one or more new lesions also constitutes PD.

Stable disease (SD) – Neither sufficient shrinkage to qualify for PR nor sufficient increase to qualify for PD taking as references the smallest sum LD since the treatment started.

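### The mandatory day-22 biopsy may excise a RECIST target lesion, and no rule stops that removal from scoring as a partial response or hiding progression at week 10

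*Combined protocol and SAP*

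**What the plan says.** **The biopsy.** Section 5.7.1 allows three techniques, depending on where the tumour lies: "the biopsy can be a core, excisional, or punch". Section 6.5.2 repeats that "A mandatory (excisional, punch or CT-guided) biopsy will be obtained", and the day-22 visit list in Section 7.4.2 has "Mandatory Fresh Tumor biopsy (excisional, punch, or CT-guided". The lesion must be accessible and safe to sample, and one site is ruled out: "Lung metastases should not be biopsied due to risk of pneumothorax". None of these passages mentions target lesions.

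**Eligibility.** Section 4.1.5 asks for "disease that is measurable by RECIST v1.1 criteria", and Section 4.1.6 asks for a tumour that can be biopsied. Nothing requires these to be different lesions.

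**Target lesions.** Section 7.8.2 starts from "All measurable lesions up to a maximum of 5 lesions total (and a maximum of two lesions per organ". It then selects on size, growth, representativeness and suitability for repeated measurement. A planned biopsy site is not listed as a reason to leave a lesion out.

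**Scoring.** PR in Section 7.8.3 is "At least a 30% decrease in the sum of the LD of the target lesions", relative to baseline. Target-lesion CR is disappearance of all targets. PD is a rise of at least 20% and 5 mm over the smallest sum so far, counting baseline. No rule says how to score a target that was surgically removed.

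**The concern.** The baseline scan is taken in the 21 days before treatment, the biopsy falls on day 22 (±2), and the first on-study scan is at day 64 (Section 6.3.6). A lesion can therefore be in the baseline sum and physically gone at the first response assessment. Superficial lesions of 10 mm or more can be measurable (Section 7.8.1), and these are the ones suited to bedside excision.

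Two secondary endpoints use the sums: ORR at week 10 and the 27-week PFS rate. Section 9.2 expects a response rate close to zero in these patients without the study drug's effect. Even one apparent response would therefore be read as a signal, and here a protocol-mandated procedure could have produced it.

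**Working it through.** **1. The plan's own intervals.** Section 9.2 gives exact 95% intervals for n = 10 of (0, 0.31) with no responses and (0, 0.45) with one. Clopper-Pearson gives:

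- 0/10: upper limit 1 − 0.025^(1/10) = 0.3085.
- 1/10: lower limit 1 − 0.975^(1/10) = 0.0025; upper limit 0.4450.

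Both reproduce. One false PR moves ORR from 0% (0 to 0.309) to 10% (0.003 to 0.445). Two would give 2/10 (0.025 to 0.556).

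**2. When excision alone scores as PR.** Let s be the excised lesion's share of the baseline sum and g the proportional growth of the remaining targets. PR is scored when (1 − s)(1 + g) ≤ 0.70, that is, s ≥ 1 − 0.70/(1 + g).

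- g = 0: s ≥ 0.30
- g = 0.10: s ≥ 1 − 0.70/1.10 = 0.364
- g = 0.19: s ≥ 1 − 0.70/1.19 = 0.412

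For k equal-sized targets with one removed, s = 1/k:

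| k | Fall in sum if the rest are unchanged | Target-lesion score | Change in the rest at which PR is still met |
|---|---|---|---|
| 1 | 100% | CR criterion for targets | none left |
| 2 | 50% | PR | growth up to 40% (0.50 × 1.40 = 0.70) |
| 3 | 33.3% | PR | growth up to 5% (0.667 × 1.05 = 0.70) |
| 4 | 25% | not PR | shrinkage of 6.7% or more (0.70/0.75 = 0.933) |
| 5 | 20% | not PR | shrinkage of 12.5% or more (0.70/0.80 = 0.875) |

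A PR overall also needs no new lesion and no non-target progression (Section 7.8.4). Section 7.8.5 requires confirmation more than 4 weeks later. An excised lesion is still absent then, so confirmation tests only whether the rest has held.

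**3. When it counts as CR.** Section 7.8.4 also requires all non-target lesions to disappear. A false overall CR therefore needs a patient with no other target or non-target disease.

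**4. Effect on PD.** Take three 20 mm targets (baseline 60 mm), one excised, 40 mm left.

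- At week 10 the smallest recorded sum is still the 60 mm baseline, because there is no scan at day 22. The PD threshold is 60 × 1.2 = 72 mm. The two remaining lesions must grow from 40 to 72 mm, or 72/40 − 1 = 80%.
- If they reach 50 mm at week 10, the plan's sum has gone from 60 to 50 mm (−16.7%, stable). With the excised lesion removed from baseline it has gone from 40 to 50 mm (+25%, +10 mm), which is PD.
- If week 10 records 40 mm, that becomes the reference and the next threshold is 40 × 1.2 = 48 mm. That is 24 mm per lesion, the same as 72/3 = 24 mm, so no earlier PD results.

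**5. Frequency.** The documents do not say how often excision would remove a sufficiently large target. If a share q of patients had such an excision and met the other conditions (an assumption), the chance of at least one false response in 10 is 1 − (1 − q)^10: 40% for q = 0.05, 65% for q = 0.10, and 89% for q = 0.20.

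**The case against.** The strongest case on the other side has five parts.

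- **Indirect safeguards.** Section 7.8.2 asks for lesions suited to repeated measurement, leaves out stable or regressing ones, and caps targets at two per organ. An investigator might therefore avoid a lesion due for excision, and a patient with several skin deposits would have untargeted ones to biopsy. This stands in part. The text never says so, and the cap also keeps target sets small, so that one lesion is a larger share of the sum.
- **Demanding conditions.** With three equal targets, more than 5% growth in the other two cancels the PR. This stands for three targets. With two, the remaining lesion can grow 40% and PR is still met.
- **Technique.** Core and punch biopsies are equally allowed and usually leave the lesion in place. This stands, and it is why no frequency can be claimed.
- **RECIST 1.1 itself.** Sections 7.8.1, 7.8.3 and 7.8.5 refer to the published criteria for details. Whether these cover a removed lesion cannot be checked from the documents. The protocol's own rules do not, and a research biopsy every patient must have deserves an explicit line. The Section 5.5 note shows the issue was recognised elsewhere: for exceptional radiation or minor surgery it requires measurable disease outside the treated field.
- **Limited stakes.** The primary endpoint is histological conversion, and ORR is tabulated with an interval and has no decision rule (Section 9.3). This stands and limits the severity.

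A reader might also infer that excision brings PD forward, because the threshold drops from 72 to 48 mm. The documents do not support that: the sum drops in step, the growth needed per lesion is the same, and at week 10 the error runs the other way. Nor does removing a patient's only target automatically give a CR, since non-target disease must be gone too.

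**Conclusion.** The gap is real and should be closed. Under the rules as written, excising a target lesion worth at least 30% of the baseline sum scores as PR when the other lesions are about stable and there is no new lesion or non-target progression. In practice this concerns patients with one to three targets, or with one dominant target. The same omission can mask progression at week 10, by up to 80% growth of the remaining lesions in the three-lesion example.

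The reach is limited to ORR and the lesion sums behind 27-week PFS; the primary conversion endpoint and its error rates are untouched. The size is one false response among about 10 patients: 0/10 (0 to 0.31) becomes 1/10 (0.003 to 0.445). This rests on two assumptions: that excision of a target does occur, at a rate the documents do not give, and that sites score from the protocol's text. It does not follow that the trial's response rate will be wrong, only that the plan does not prevent it.

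**What to change.** In Sections 5.7.1 and 7.8.2:

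1. Name the planned biopsy lesion at baseline and record it as non-target whenever another measurable lesion exists. Its removal then cannot create a PR.
2. If a target lesion is nevertheless excised, remove it from the baseline sum and from every later sum, for both response and PD.
3. If no measurable target remains, keep the patient in the ORR denominator as a non-responder, and report a sensitivity ORR excluding such patients. Excluding them from the main analysis instead would cost 10% of a 10-patient denominator each time.

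The cost is a few sentences and one CRF field for the biopsy lesion. The downside is occasionally one fewer target lesion and a slightly less favourable ORR. Treatment and the primary analysis do not change. If biopsies have already been taken, the same sums can be rebuilt from the biopsy and lesion records and reported as sensitivity analyses of ORR and PFS.

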5.7.2 Peripheral Blood for Translational Endpoints

Approximately 50 mL of peripheral blood will be collected for the purpose of analyzing the translational endpoint outlined in section 6.5.1.

5.8 Duration of Therapy

In the absence of treatment delays due to AE, treatment may continue for up to 27 weeks or until:

- Disease progression,
- Inter-current illness that prevents further administration of treatment,
- Unacceptable AE(s),
- Pregnancy,
- Patient decides to withdraw from study treatment, **OR**
- General or specific changes in the patient's condition render the patient unacceptable for further treatment in the judgment of the investigator,
- Subject completes maximum number of treatment cycles (i.e., 9 cycles / 27 weeks of treatment) allowed per protocol,
- Subject is lost to follow-up.

Subjects receiving clinical benefit after the study assessment period (6 months) may continue pembrolizumab off-study at the investigator's discretion, as per standard of care guidelines.

5.9 Duration of Follow Up

Patients who have not progressed on pembrolizumab plus entinostat after 27 weeks of treatment will be followed every 3 months (\pm 2 weeks) for up to 2 years following treatment initiation (C1D1). Follow ups include phone calls or visits. The following information will be recorded: (a) details regarding systemic treatment for their melanoma that they are currently on (type, response if any, duration on treatment), (b) whether they have progressed (and when) from current PD-1 inhibitor treatment, (c) whether treatment-related AEs that patients may have developed during the 27 weeks of entinostat-pembrolizumab treatment have resolved, and when, (d) whether they are alive or not; if dead, precise date of death.

Patients who have progressed on pembrolizumab plus entinostat within the 27 weeks of the study duration will be followed every 3 months (\pm 2 weeks) for up to 2 years following treatment initiation. Follow up may include phone calls or visits. The following information will be recorded: (a) systemic treatment for their melanoma they are currently on (type, response if any, duration on systemic anticancer treatments, systemic anticancer treatment-related grade 2 or higher AEs), (b) whether treatment-related AEs that patients may have developed during the year of entinostat-pembrolizumab treatment have resolved, and when, (c) whether they are alive or not; if dead, precise date of death.

Patients removed from study treatment for unacceptable AEs will be followed for resolution or stabilization of the adverse event(s). All patients (including those withdrawn for AEs) should be followed after removal from study treatment as stipulated in the protocol.

5.10 Study Withdrawal

If a patient decides to withdraw from the study treatment (and not just from protocol therapy), an effort should be made to complete and report study assessments as thoroughly as possible. At the time of withdrawal, the investigator should attempt to establish as completely as possible the reason for the study treatment withdrawal.

1. The patient should be asked if they are willing to allow for the abstraction of relevant information from their medical record to meet the long-term follow-up (e.g., survival endpoints) objectives outlined in the protocol.
2. A complete final evaluation at the time of the patient's study treatment withdrawal should be obtained with an explanation of why the patient is withdrawing from the study.
3. If the patient is noncompliant and does not return for an end of study follow-up assessment, this should be documented in the eCRF as lost to follow-up.
4. If the reason for removal of a patient from the study is an AE, the principal specific event will be recorded on the eCRF per reporting guidelines.

Note: Inappropriately high number of patient withdrawals from protocol therapy or from the study (i.e. >4 patients) can render the study un-interpretable; therefore, unnecessary withdrawal of patients should be avoided.

